### Screening Assessments

For Part 1 only (as described above), genotyping may be performed first and only subjects that are found to have the genetic variant of interest will be invited back to complete the remaining screening assessments.

For Part 2 only, genotyping is performed as part of the overall screening assessments, since all subjects are genetically eligible to participate in this study.

The screening assessments (Visit 1) will determine the full eligibility of each subject and should be performed within 8 weeks of the planned dosing date (or up to 12 weeks if agreed by the Sponsor Medical Monitor). Refer to Protocol Section 4.3 for rescreening guidelines.

The following screening assessments are required for ALL subjects:

- Demographics
- Medical/surgical history
- Concomitant medication
- Genotyping (only required if not already available from a Sponsor-approved laboratory. Genotyping results will be received to confirm eligibility prior to other screening activities in Part 1 only)
- Pregnancy test (for women of child-bearing potential only)
- AEs
- Vital signs
- Biochemistry/haematology
- Serum CFI level (only required if not already available from a Sponsor-approved laboratory)

■ [REDACTED]

- Ophthalmic examination\*
- CFP
- FAF
- OCT macula

- CNV assessment; may be based on history or be performed using multimodal imaging techniques, which may include OCT, OCT-A and/or FA. Further details are provided in the Central Imaging Manual.

- BCVA using ETDRS\*
- Low luminance visual acuity (LLVA) using ETDRS for LLD\*
- MNRead
- VFQ-25
- FRI Index

\*The screening period may be extended up to a maximum of 12 weeks, if agreed by the Sponsor Medical Monitor. If the screening period is greater than 8 weeks, haematology/biochemistry, standard ophthalmic exam and BCVA/LLVA should be repeated; other assessments may be performed at the investigator's discretion.

### 6.1.2 Randomisation (Telephone Call)

Randomisation will occur upon confirmation of eligibility. The Investigator will follow the randomisation procedure (IRT), as described in Section 3.4, and inform the subject of treatment allocation (GT005 or untreated control).

For subjects randomised to the untreated control, Day 1 will be defined as the day following randomisation for the calculation of Week 5 to 96 visits.

For subjects randomised to GT005, the day of surgery is described as Day 1 in the study timeline (Section 6.1.3). The interval between randomisation and Day 1 must be sufficient to allow arrangements to be made for surgery, and to prepare the subject, as appropriate, for treatment. Randomisation therefore resides within the interval between screening and surgery, which should not exceed 8 weeks, unless agreed by the Sponsor Medical Monitor, who may approve an extension for up to a maximum of 12 weeks.

The Investigator will ask the subject if any changes have occurred since the screening visit and record in the eCRF:

- AEs
- Concomitant medication

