#### 4.3 Screen Failures and Replacements

Subjects who are screened but not randomised will be classed as Screen Failures and will be replaced. A subject can be screened twice if the reason for ineligibility is transient (e.g., a cataract requiring cataract extraction), to allow the 8-week time interval between baseline assessment of the Screening Visit and dosing to be maintained (or up to 12 weeks if agreed by the Sponsor Medical Monitor). If the screening period is extended past the original 8-week screening period, a standard ophthalmic exam, haematology/biochemistry and visual acuity (BCVA and low luminance visual acuity [LLVA]) assessments should be repeated.

If a subject is rescreened **within** the 8-week time interval between the screening visit and dosing, only the standard ophthalmic exam and visual acuity (BCVA and LLVA) needs to be repeated provided the original results from the other screening assessments were acceptable for study inclusion. If a subject is rescreened **outside** of the 8-week screening period, all screening assessments should be repeated with the exception of genotyping and serum CFI.

Subjects who are withdrawn from the study after randomisation will not be replaced. The reason for the subject's withdrawal from the study will be recorded in the electronic case report form (eCRF).

Subjects who are randomised to GT005 treatment but do not subsequently get dosed, should be offered the option to continue in the study following the same visit schedule as those who are allocated to the untreated control arm [Table 2]. The reason for not receiving GT005 should be recorded in the eCRF.

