#### 5.5 Measures to Minimise Bias: Randomisation and Masking

This is an open label, outcomes assessor-masked study. In Part 1, the Sponsor, Investigators, subjects, study personnel involved in the study will remain **dose-masked** to those randomised to GT005.

In Part 2, the Sponsor, Investigators, subjects, and study personnel performing clinical assessments will be **unmasked** to dose received, since only the low dose will be administered.

In order to minimise the potential impact of knowledge of treatment, the randomisation list will be kept strictly confidential, such that no aggregate statistical analyses by efficacy across the study by treatment shall be performed prior to the database lock/interim analysis (as applicable), except for those specified in the DMC charter review for the closed sessions.

For Part 1 only, unmasked study personnel will be assigned to prepare GT005 for administration; however, they will not be involved in any other aspect of the study (i.e., consent, safety/efficacy assessments, surgical procedure).

To minimise bias, all imaging endpoint assessments and grading will be performed at a CRC. All imaging efficacy assessments are to be performed in a fully-masked fashion. █████

The randomisation process is defined in Section 3.4.

Additional measures to minimise bias include standardised methodologies across participating sites, and similar visit/assessment schedule for treated/untreated subjects.

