### 2.1.1.2 Baseline and post-Baseline

*Baseline* (Day 1) is defined as

- the day following randomization for subjects randomized to untreated control
- the day of successfully receiving GT005 administration for subjects randomized to GT005
- or the latest surgery date for subjects who were randomized to GT005 but failed to receive GT005 administration on the first attempt to surgery (if applicable)

The baseline value for efficacy and safety variables is the last available value (scheduled or unscheduled) collected prior to the date of *Baseline*, or on the date of *Baseline* but prior to the time of GT005 administration for GT005 treatment groups.

All data collected after the date of *Baseline* are defined as post-baseline. The *study day* for a baseline or post-baseline scheduled or unscheduled visit is defined as:

$$\text{Study day} = \begin{cases} (\text{Date of visit}) - (\text{Date of randomization}) & \text{Untreated} \\ (\text{Date of visit}) - (\text{Date of treatment administration}) + 1 & \text{GT005} \end{cases}$$

The *study day* for a scheduled or unscheduled visit before baseline is defined as

$$\text{Study day} = \begin{cases} (\text{Date of visit}) - (\text{Date of randomization}) - 1 & \text{Untreated} \\ (\text{Date of visit}) - (\text{Date of treatment administration}) & \text{GT005} \end{cases}$$

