### 2.1.1.4 Unscheduled visits

For unscheduled visits, the analysis visits will be derived with windowing where appropriate (e.g., Visit  $3 \pm 3$  days) as per the protocol. For scheduled visits, the analysis visits will be the actual (reported) visit number.

Data collected at unscheduled visits will not be used in 'by-visit' tabulations, graphs or analyses unless it can be mapped to a missed scheduled visit with the window specified per the protocol. If multiple unscheduled visits are allocated to the same missed scheduled visit:

- The unscheduled visit closest to the missed scheduled visit will be used
- If there are multiple unscheduled visits with the same distance to the missed scheduled visit, the latest one will be used

For analyses showing abnormalities, data from unscheduled visits will be considered individually, without mapping to a main visit.

For analyses based on all post-baseline values such as averages over a given period summaries of maximum/minimum values, data collected at unscheduled visits will be included.

All data collected at unscheduled visits will be listed.

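### GT005 visits are counted from surgery and control visits from the day after randomisation, while both arms usually keep the screening FAF as baseline, so GT005 change to Week 48 contains extra untreated growth that no planned table or analysis reveals

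*Protocol*

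**What the plan says.** **Two clocks.** Protocol 6.1.2 sets the control clock: for the "untreated control, Day 1 will be defined as the day following randomisation for the calculation of Week 5 to 96 visits". Section 3.4.2 repeats it. For the other arm, 6.1.2 says: "For subjects randomised to GT005, the day of surgery is described as Day 1 in the study timeline". It adds: "The interval between randomisation and Day 1 must be sufficient to allow arrangements to be made for surgery". Screening to surgery is limited to 8 weeks, or 12 with the Sponsor Medical Monitor's agreement. The study-day formulas in SAP 2.1.1.2 follow the same two clocks.

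**One baseline rule.** SAP 2.1.1.2: "The baseline value for efficacy and safety variables is the last available value (scheduled or unscheduled) collected prior to the date of" Day 1, or on Day 1 before dosing. The readable FAF rows of Protocol Tables 1 and 2 show no FAF between screening and Day 1, and the legible pre-surgery list in 6.1.3.1 has none. If screening runs past 8 weeks, FAF is not among the required repeats (6.1.1). After randomisation a repeat FAF is required only when dosing is deferred and more than 12 weeks have passed since screening (6.1.3.2; Table 1, footnote 3).

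**Analysis.** SAP 2.1.1.4: "For scheduled visits, the analysis visits will be the actual (reported) visit number". The MMRM in SAP 2.5.2 and the variant in 5.4.1 have no term for elapsed time. The summary measure (SAP 1.2.1) is the difference in means as a percentage of control. Sensitivity and supplementary analyses (2.5.5, 2.5.6) are both marked as not applicable.

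**Stated safeguard.** Protocol 5.5 lists among its measures against bias a "similar visit/assessment schedule for treated/untreated subjects".

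**The concern.** Let S be the weeks from baseline FAF to randomisation and D the weeks from randomisation to surgery. Change to Week 48 then spans about S + 48 weeks in controls and S + D + 48 weeks in GT005. The extra D weeks precede dosing, so growth in them cannot be an effect of GT005, yet it is counted in the GT005 mean.

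SAP 2.5.3 asks for the effect attributable to GT005. With no inferential testing planned (Protocol 9.4.2), the percentage and its 90% confidence interval are the main efficacy output. The extra interval shifts that percentage against GT005 and lowers the interval's coverage of the treatment effect over 48 weeks. Adjusting for baseline lesion area corrects for size, not elapsed time. The ±7-day visit windows apply to both arms from Week 12 and do not cancel D. A reader would have to reconstruct the intervals from the GA-area and surgery listings (SAP 2.6.2, 2.4.1).

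A related gap is that SAP 2.1.1.2 covers "the latest surgery date for subjects who were randomized to GT005 but failed to receive GT005 administration on the first attempt to surgery" but gives no Day 1 for those who never reached surgery. Protocol 4.3 lets undosed GT005 subjects "continue in the study following the same visit schedule as those who are allocated to the untreated control arm", and they belong to the Full Analysis Set.

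**Working it through.** **Inputs from the documents.** Control growth 2.1 mm² over 48 weeks, SD 1.3 mm² and dropout up to about 10–12% (Protocol synopsis, sample size); 90% confidence intervals (9.3); 2:1 allocation (3.1); about 202 subjects, of whom about 10 are on high dose (9.1).

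**Assumptions.** Linear untreated growth; D shown as a range because no mean is given; a true effect of 25%, because the design effect and power are redacted. One-sided 5%, 80% power and a 25% effect give a total of 200 (10% dropout) or 205 (12%). That fits 202, but so do 27% with 85% power (200 or 205) and 30% with 90% power at 12% dropout (198). The design effect therefore cannot be identified. The plan states no figure for the interval, so there is none to reproduce.

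**Bias.** Weekly growth g = 2.1/48 = 0.04375 mm². Control change = g(S + 48). With true fractional reduction e, GT005 change = g(S + D) + 48g(1 − e). The excess in GT005 is gD. Control Day 1 is the day after randomisation, which lowers this by g/7 = 0.006 mm².

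**Reported reduction from D alone** = (48e − D)/48.

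**Coverage of the 90% interval.** Evaluable subjects = 192 × 0.88 = 169, split 112.6 and 56.3. SE = 1.3 × √(1/112.6 + 1/56.3) = 0.212. Coverage = Φ(1.645 − gD/SE) − Φ(−1.645 − gD/SE). At half that size SE = 0.300.

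| D (weeks) | Bias (mm²) | % of 2.1 | True 25% reads as | True 0% reads as | Coverage, planned size | Coverage, half size |
|---|---|---|---|---|---|---|
| 1 | 0.044 | 2.1 | 22.9% | −2.1% | 0.893 | 0.896 |
| 2 | 0.088 | 4.2 | 20.8% | −4.2% | 0.871 | 0.886 |
| 4 | 0.175 | 8.3 | 16.7% | −8.3% | 0.787 | 0.843 |
| 6 | 0.263 | 12.5 | 12.5% | −12.5% | 0.656 | 0.774 |

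D = 6 is near the ceiling without the 12-week extension. If an assumed 10% of GT005 subjects are never dosed and follow the control clock, the bias is 0.9gD = 0.04, 0.08 and 0.16 mm² at D = 1, 2 and 4.

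**Does a supplementary model remove it?** The model uses actual FAF dates, a common untreated slope, and a step and a slope change for each GT005 dose from Day 1. It was checked by exact generalised least squares with 113 vs 56 subjects, S uniform on 1–3 weeks, assumed baseline SD 4 mm² and assumed FAF error SD 0.15 or 0.30. The true difference is −0.25 × 2.1 = −0.525.

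- It returns −0.525 at D = 1, 2 and 4, with SE 1.00, 1.01 and 1.03–1.04 times the unadjusted SE.
- With onset delayed to Week 8 it returns −0.52. A slope change without the step returns −0.70 to −1.03.
- With a +0.10 mm² shift at Day 1 (truth −0.425) it returns −0.425. Without the step the result is −0.64 to −1.06.

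Simulation (400 REML runs per setting, FAF error SD 0.2, Monte Carlo error of coverage 0.015–0.02):

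| Setting | Unadjusted: mean (coverage) | Step and slope: mean (coverage) |
|---|---|---|
| D = 2 | −0.433 (0.885) | −0.512 (0.878) |
| D = 4 | −0.364 (0.840) | −0.533 (0.905) |

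At D = 4 the simulated coverage of 0.840 exceeds the formula's 0.787. Part of the gap is that the simulated bias was 0.525 − 0.364 = 0.161. With that bias and the simulated SE of 0.216, the formula gives 0.81.

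**The case against.** **D is not stated, and the larger figures need D of 4 or more.** This stands. Protocol 7.3.9 contemplates surgery within 4 weeks of the BCVA; with an assumed S = 2 that means D of 2 or less, where coverage is 0.87 or better. BCVA is an imperfect guide, though, because past 8 weeks it must be repeated and FAF need not be. Not knowing D is the reason to tabulate it.

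**The study is being terminated, so the planned size may not be reached, and no testing is planned.** This is fair for coverage, hence the half-size column. The bias in mm² and in percent does not depend on sample size, and the SAP still plans this analysis for the CSR as data allow. The bias cannot create an apparent benefit, but a null product reading as 8% worse than control would still mislead.

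**Some subjects may have a later baseline FAF, and parts of both documents are redacted.** This stands. Rescreening, investigator discretion, deferral past 12 weeks or pre-operative imaging of unstated modality (1.6.1.2) could reset the baseline. The finding concerns the ordinary subject, the readable schedule and the legible summaries.

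**The extra model is more than is needed.** Partly fair. At D = 2 it brings no coverage gain, although the point bias shrinks. Its percentage uses 48 weeks of control growth and the primary's uses S + 48, so the two analyses should be compared in mm². It drops the baseline-area terms, and about 10 high-dose subjects will give an imprecise estimate under any model. Protocol 5.5 promises a similar schedule, not an identical one, so it is weakened rather than contradicted.

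**Conclusion.** The concern holds and should be fixed. For the ordinary subject, the GT005 mean change to Week 48 includes about D weeks more pre-dose growth than the control mean, and nothing in the legible plan measures or corrects this. The bias is 0.044 mm² per week of mean D, about 2% of control growth, always against GT005. It is modest at D of 1–2 weeks and material at 4 (0.18 mm², 8%; 90% interval coverage about 0.79 by formula and 0.84 by simulation at the planned size).

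These figures rest on linear growth at the planned control rate, an assumed D, and few repeated baseline FAFs. The mechanism is certain from the text; the actual size is unknown until the intervals are tabulated. No loss of power and no link to the futility decision is claimed. The missing Day 1 for never-operated subjects is a separate, minor omission.

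**What to change.** 1. **SAP 2.5.2.** Add a table by arm of the intervals from baseline FAF to Day 1 and from baseline FAF to Week 48 (mean, SD, median, range), with the number of subjects whose baseline FAF was a repeat.
2. **SAP 2.5.6, specified in 5.4.1.** Add one supplementary model: GA area on actual FAF dates; random intercept and slope by subject; a common untreated slope on weeks since baseline FAF; and for each GT005 dose a step and a slope change from Day 1, both zero before it. Set FAFs after alternative GA therapy to missing, as in Table 1-2. Report step + 48 × weekly slope change with a 90% confidence interval, in mm² and as a percentage of 48 weeks of control growth.
3. **SAP 2.1.1.2.** State that subjects randomised to GT005 who never had surgery stay in their randomised arm, with Day 1 the day following randomisation.
4. **Primary MMRM.** Leave unchanged.

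The cost is SAP wording, one table and one model. FAF and surgery dates are already collected, and no visit changes. The model assumes near-linear untreated growth and a common pre-treatment slope. The step must stay in: Protocol 1.6.1.1 reports pigment changes visible on FAF, mostly first seen at Week 12, and without the step a late onset or a post-surgical FAF shift distorts the estimate badly. In the checks above the step-and-slope model widened the SE by 0–4%.

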### 6.1.3 Visit 2, Day 1 (Surgical Site)

Visit 2 will only apply to subjects randomised to GT005.

This visit will be performed at a centralised surgical site and will be split in three parts: pre-surgery, surgery, and post-surgery assessments.

#### 6.1.3.1 Pre-surgery (Surgical Site)

Pre-surgical assessments will include any local requirements of the surgical site. Pre-surgery is defined as the time between randomisation and surgery. The following assessments are required pre-surgery:

- Medical/surgical history
- Concomitant medication
- Pregnancy test
- Vital signs
- AEs
- [REDACTED]
- [REDACTED]
- Pre-surgical ocular safety check to verify there are no new ocular adverse events that would halt surgery
- Snellen visual acuity (refer to Section 7.3.9)

#### 6.1.3.2 Surgery – Day 1 (Surgical Site)

##### Deferred GT005 Delivery

In the event the GT005 administration is deferred during the surgical procedure (e.g., due to an AE occurring during surgery) the administration surgery may be rescheduled within 10 weeks of the original surgery date if agreed by the Sponsor Medical Monitor. Additionally, if the time from screening is extended past 12 weeks, in case of GT005 deferral, FAFs will be repeated, in addition to standard ophthalmic examination, haematology and biochemistry, and visual acuity (BCVA and LLVA).

The following assessments are required during surgery:

- [REDACTED]
- AEs
- Concomitant medications
- [REDACTED]
- [REDACTED]
- [REDACTED]

The procedure for the administration of GT005 is described in Section 5.4 and in the Surgical Manual.

■ [REDACTED]  
■ [REDACTED]  
■ [REDACTED]

#### 6.1.3.3 Post-surgery – Day 2 (Surgical Site)

The following assessments are required one day post-surgery:

- Concomitant medication

■ [REDACTED]

- Vital signs

- AEs/

- Ophthalmic examination

■ [REDACTED]

- OCT macula

#### 6.1.4 Day 3 (Telephone call)

Day 3 telephone call will only apply to subjects randomised to GT005.

The following information will be recorded:

- Concomitant medication

■ [REDACTED]

- AEs

#### 6.1.5 Visit 3 (Week 1) (Surgical Site)

Visit 3 (Week 1) will only apply to subjects randomised to GT005.

The following assessments will be performed:

- Concomitant medication

■ [REDACTED]

- AEs

- Vital signs

- Ophthalmic examination

- BCVA using ETDRS

- OCT macula

■ [REDACTED]

- OCT-A and/or FA if clinically indicated (if a subject converts to wet AMD)

#### 6.1.6 Week 2 (Telephone call)

Week 2 telephone call will only apply to subjects randomised to GT005.

The following information will be recorded:

- Concomitant medication

■ [REDACTED]

- AEs

#### 6.1.7 Visit 4, Week 5 (Local or Surgical Site for GT005 Subjects/Telephone Call for Untreated Control Subjects)

At Week 5, subjects may choose to attend a local investigative site or surgical site for clinical assessments and ophthalmic imaging, with review of images by both the local site Investigator and the Surgeon.

Subjects allocated to untreated control will receive a telephone call from their local investigative site to review concomitant medications and AEs.

Visit 4 (Week 5) assessments listed below will only apply to subjects randomised to GT005.

The following assessments will be performed:

- Concomitant medication
- [REDACTED]
- Vital signs
- AEs
- Biochemistry/haematology
- [REDACTED]
- Ophthalmic examination
- OCT macula
- [REDACTED]
- BCVA using ETDRS
- CFP
- FAF
- OCT-A and/or FA if clinically indicated (if a subject converts to wet AMD)
- [REDACTED]
- [REDACTED]
- [REDACTED]

#### 6.1.8 Visit 5, Week 8 (Local or Surgical Site)

Visit 5 (Week 8) assessments listed below will only apply to subjects randomised to GT005:

- Concomitant medication
- AEs
- Ophthalmic examination
- [REDACTED]
- BCVA using ETDRS
- OCT-A and/or FA if clinically indicated (if a subject converts to wet AMD)

#### 6.1.9 Visit 6, Week 12 (Local or Surgical Site)

The following assessments will be performed for ALL subjects unless otherwise specified:

- Concomitant medication
- [REDACTED]
- AEs
- [REDACTED]
- Biochemistry/haematology
- [REDACTED]
- Ophthalmic examination
- FAF
- OCT macula
- [REDACTED]
- [REDACTED]
- [REDACTED]
- BCVA using ETDRS
- LLVA using ETDRS for LLD
- OCT-A and/or FA if clinically indicated (if a subject converts to wet AMD)
- [REDACTED]
- [REDACTED]
- [REDACTED]

#### 6.1.10 Visit 7, Week 24 (Local or Surgical Site)

The following assessments will be performed for ALL subjects unless otherwise specified:

- Concomitant medication
- Vital signs
- AEs
- Biochemistry/haematology
- [REDACTED]
- [REDACTED]
- Ophthalmic examination
- FAF

- OCT macula
- [REDACTED]
- [REDACTED]
- [REDACTED]
- BCVA using ETDRS
- LLVA using ETDRS for LLD
- MNRead
- VFQ-25
- FRI Index
- OCT-A and/or FA if clinically indicated (if a subject converts to wet AMD)
- [REDACTED]
- [REDACTED]
- [REDACTED]

#### 6.1.11 Visit 8, Week 36 (Local or Surgical Site)

The following assessments will be performed for ALL subjects unless otherwise specified:

- Concomitant medication
- AEs
- Ophthalmic examination
- FAF
- OCT macula
- [REDACTED]
- [REDACTED]
- [REDACTED]
- BCVA using ETDRS
- LLVA using ETDRS for LLD
- MNRead
- VFQ-25
- FRI Index
- OCT-A and/or FA if clinically indicated (if a subject converts to wet AMD)
- [REDACTED]
- [REDACTED]
- [REDACTED]

